### **b) Inclusion and Exclusion Criteria**

Inclusion criteria: patients scheduled to undergo laparoscopic gastric sleeve gastrectomy, from 18-65 years of age, with a  $BMI > 35 \text{ kg/m}^2$ .

Exclusion criteria: contraindications to administration of local anesthesia (e.g. local anesthetic allergy), as well as a contraindication/allergy to acetaminophen or ketorolac, and history of substance abuse or chronic opioid use, coagulopathy, patients receiving systemic anticoagulation, local infection, and ASA 4.

### **c) Number of Subjects**

**110**

The sample size was determined by *a priori* power analysis, two-tailed, with effect size of 0.7 (mild-moderate effect), alpha error 0.05, power 0.95.

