### 4)Resources Available to Conduct the Human Research

For n=110, the feasibility of recruitment is manageable as we perform 5-10 sleeve gastrectomies per week on average. Recruitment will be done through a coordination of the operating schedule and the surgeon's office. Patients presenting for preoperative visits at the preoperative testing clinic will be approached. Patients routinely are seen by anesthesiologists at the preoperative testing clinic as part of their anesthetic evaluation. Patients will be approached by research personnel only if the patients are agreeable to the study and details of the study will be explained. The consent will be obtained in the pre operative testing clinic or in the pre operative holding area after all questions are thoroughly answered. The staff members on this protocol are all employees of Mount Sinai and will either be a resident or attending

|   |  |
|---|--|
| Protocol Title:                           | QUADRATUS LUMBORUM II BLOCK VS CONVENTIONAL THERAPY ALONE FOR LAPAROSCOPIC SLEEVE GASTRECTOMY  |
| Principal Investigator Name/Contact Info: | [name] MD
[contact]   |
| Primary Contact Name/Contact Info         | [name] MD
[contact]
[contact]
[name] MD
[contact]
[contact]
[name] MD
[name] MD
[name] DO
[name] MD |
| Date Revised:                             | 1/10/2018  |
| Study Number:                             | IF 2203362   |

physicians that are included on the IRB protocol. There are seven primary members of the research personnel:

a) [name]. – Roles for [name] in this study include serving as primary investigator responsible for study design and planning, data collection, subject recruitment, manuscript writing and preparation, data analysis, safety monitoring, and responding to adverse events and/or complications. He is certified in PPHS/IRB protocols, all Citi/IRB required training in human subject protection, and has prior clinical research experience. He is also a board certified anesthesiologist and assistant professor of anesthesiology with the Icahn School of Medicine and the Mount Sinai Health System.

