## 5) Study Design

### b) Recruitment Methods

This project will be a prospective double blinded randomized control trial.

Recruitment will be done through a coordination of the operating schedule and the offices of bariatric surgeons who have agreed to allow us to approach their patients regarding recruitment for the study. Patients presenting for preoperative visits at the preoperative testing clinic at St. Luke's Hospital will be approached. Patients routinely are seen by anesthesiologists at the pre operative testing clinic as part of pre operative anesthetic evaluation. Patients will be approached by research personnel only if the patients are agreeable to the study and details of the study will be explained. The consent will be obtained in

|   |   |  |
|---|---|--|
|  | Protocol Title:                           | QUADRATUS LUMBORUM II BLOCK VS CONVENTIONAL THERAPY ALONE FOR LAPAROSCOPIC SLEEVE GASTRECTOMY  |
|   | Principal Investigator Name/Contact Info: | [name] MD
[contact]   |
|   | Primary Contact Name/Contact Info         | [name] MD
[contact]
[contact]
[name] MD
[contact]
[contact]
[name] MD
[name] MD
[name] DO
[name] MD |
|   | Date Revised:                             | 1/10/2018  |
|   | Study Number:                             | IF 2203362   |
|   |   |  |

the pre-operative testing clinic or in the pre operative holding area after all questions are thoroughly answered.

Patients who meet the inclusion criteria will be recruited. The team will finalize participation and ask the subject to sign the study consent forms. All patients will be provided with copies of the IRB protocol and consent if they wish to have it. Copy of the consent form will be sent in a secured email to the potential subject. The email will be secured by entering in [SECURE] in the e-mail subject line. Once recruited blinding assessments will be done by the study team.

Patients will be assigned randomly using a computer- generated table of numbers to either QL 2 block (QL group) or wound infiltration (conventional therapy group). The anesthesia team will perform all blocks. The resident anesthesiologist will know the group allocation but will not be involved in the study. Conventional therapy consists of the injection of 30 mL of bupivacaine 0.25% directly into the incision sites by the surgeon at the end of the procedure.

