### e) Study Endpoints

Primary outcome: The amount of opioid consumption (in mg IV morphine equivalents) postoperatively during the first 48 hours after the procedure.

Secondary outcome: VAS pain scores on arrival to PACU and at 1, 2, 24, and 48 hours. VAS scores on ambulation on the floors. Extent of blockade as determined by pin prick, itching, nausea, vomiting in PACU.

Respiratory rate, heart rate, and blood pressure will be recorded on arrival, 1 hour after arrival to PACU and then on departure from PACU.

Time to first dose of opioid administration, PACU length of stay, location of pain.

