## 8)Potential Benefits to Subjects

|   |  |
|---|--|
| Protocol Title:                           | QUADRATUS LUMBORUM II BLOCK VS CONVENTIONAL THERAPY ALONE FOR LAPAROSCOPIC SLEEVE GASTRECTOMY  |
| Principal Investigator Name/Contact Info: | [name] MD
[contact]   |
| Primary Contact Name/Contact Info         | [name] MD
[contact]
[contact]
[name] MD
[contact]
[contact]
[name] MD
[name] MD
[name] DO
[name] MD |
| Date Revised:                             | 1/10/2018  |
| Study Number:                             | IF 2203362   |

Benefits of QL 2 block in the context of bariatric surgery are unknown. Possible benefits that have been described in the literature include improved quality and duration of analgesia, reduced opioid consumption, reduced incidence of nausea and vomiting, and reduced incidence of constipation. There may not be any benefits.

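### Does calling 0.7 SD a mild-moderate effect overstate what 110 patients can detect?

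*Protocol*

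**What the plan says.** Section 5 c) Number of Subjects gives 110 and one sentence of rationale: "two-tailed, with effect size of 0.7 (mild-moderate effect), alpha error 0.05, power 0.95". Section 4 repeats the number when discussing recruitment: "For n=110, the feasibility of recruitment is manageable". Section 5 d) Study Timelines treats 110 as the number in the final analysis.

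The endpoint being powered is continuous, as section 5 e) Study Endpoints shows: "The amount of opioid consumption (in mg IV morphine equivalents) postoperatively during the first 48 hours after the procedure". No expected mean, SD or difference in mg is given.

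The control arm is active. Under section 5 b) Recruitment Methods, "Conventional therapy consists of the injection of 30 mL of bupivacaine 0.25% directly into the incision sites by the surgeon". The block arm receives the same total volume of the same solution, and section 5 f) gives both arms scheduled acetaminophen and ketorolac. On expected benefit, section 8 says "Benefits of QL 2 block in the context of bariatric surgery are unknown".

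**The concern.** The label tells the reader which effect the 95% power applies to. On the common benchmarks for a standardised mean difference (0.5 medium, 0.8 large; a convention, not something in the Protocol), 0.7 lies above medium and nearer to large. With normal data, a 0.7 SD shift means that the average block patient uses less opioid than about 76% of controls.

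Two features sharpen the worry. Both arms receive the same drug in the same amount, so the contrast is only where and how it is injected, and a smaller difference is a realistic possibility. And nothing beyond the label supports 0.7.

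What would be at stake is how a non-significant result is read. Someone who took the sentence to promise 95% power for a modest benefit might conclude that such a benefit had been excluded. In fact a true 0.5 SD benefit would be missed about one time in four, and a 0.35 SD benefit more than half the time.

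**Working it through.** **Inputs.** From section 5 c): d = 0.7, two-sided alpha 0.05, power 0.95, total 110. Section 5 b) describes random assignment to two groups without a ratio; 1:1 is assumed, so 55 per arm.

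**1. Reproducing 110.** Normal approximation:

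n per arm = 2(z₀.₉₇₅ + z₀.₉₅)² / d² = 2(1.960 + 1.645)² / 0.49 = 53.04, so 54 per arm and 108 in total.

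The two-sample t-test (noncentral t) needs 54.02 per arm, so 55 per arm and **110 in total**, an exact match. A one-sided test would give 90. The sentence therefore describes a two-sided t-test with d = 0.7 in SD units, and the arithmetic is right.

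**2. Power with 55 per arm.** The noncentrality is d√(55/2) = 5.244d. For d = 0.7 this is 3.671, and the normal approximation gives Φ(3.671 − 1.960) = Φ(1.711) = 95.6%; the noncentral t gives 95.3%. Across effects, by noncentral t:

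| True difference (SD) | Power |
|---|---|
| 0.7 | 95.3% |
| 0.6 | 87.7% |
| 0.5 | about 74% |
| 0.4 | 54.7% |
| 0.35 | 44.4% |
| 0.3 | 34.5% |

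The smallest difference detectable is 0.54 SD with 80% power, 0.62 with 90% and 0.69 with 95%.

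**3. What the lower rows show.** They are correct, but 0.5 and 0.35 SD are illustrative values that appear nowhere in the Protocol. Every trial loses power below its design effect. At the conventional 80% level this one reaches down to 0.54 SD, close to the medium benchmark.

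**4. Translating 0.7 SD into opioid use.** Relative reduction = 0.7 × (SD / control mean). If the SD were 50% to 100% of the control mean, that is 35% to 70%. The ratio is an assumption without support in the Protocol. Its upper end also sits badly with the 76% figure: Φ(0.7) = 0.758 assumes normality, and a normal distribution with SD equal to its mean puts Φ(−1) = 16% of patients below zero consumption.

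**5. What a null result would exclude.** This depends on the confidence interval, not on the label. With a t quantile of 1.98 on 108 degrees of freedom, the 95% half-width is 1.98 × √(2/55) = 1.98 × 0.1907 = 0.38 SD. An observed difference near zero would exclude 0.5 SD; an observed benefit of 0.3 SD would not, since its upper limit is 0.3 + 0.38 = 0.68 SD. The wording in section 5 c) alters neither interval.

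**The case for a change.** The strongest case for a change is that the label is part of the claim and is the only justification offered for 0.7. At 0.5 SD, a natural reading of moderate, the type II error is 26% rather than 5%, and 95% power there would take 210 patients. With the same drug and volume in both arms, an effect below 0.7 SD is quite possible, and correcting the wording costs only a few sentences.

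Part of this stands. *Mild* does not suit 0.7 SD, and moderate-to-large would be a better description. It is also true that no mg difference or SD stands behind the figure.

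The rest does not carry. The number is printed next to the adjective, so any statistically literate reader sees what was powered for. No sentence claims 95% power at a smaller effect or says that a null result will rule out a modest benefit; that misreading is predicted, not written. The active comparator does not settle the size of the effect either. The injection site is the intervention, and section 2 gives a reason to expect a difference from this very comparator, namely spread toward the paravertebral space. Section 8 goes on from the admission that benefit is unknown to list reduced opioid use among the possibilities. How a null result is to be interpreted is commonly left to a statistical analysis plan, which is not at hand.

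**Conclusion.** No change follows. The plan states no sample size or power that its design fails to deliver: 110 patients, 55 per arm under assumed 1:1 allocation, give 95.3% power for a standardised difference of 0.7 with a two-sided 5% t-test. What remains is a generous adjective beside a correct number. A different adjective, a power curve, or the mg difference and SD behind 0.7 would inform the reader but would leave the sample size, conduct, analysis and result unchanged. The figures of 74% at 0.5 SD and 44% at 0.35 SD are sound as background, but they rest on effects chosen for illustration, and the Protocol gives no basis for preferring them to 0.7.

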### **d) Study Timelines**

One year

|   |  |
|---|--|
| Protocol Title:                           | QUADRATUS LUMBORUM II BLOCK VS CONVENTIONAL THERAPY ALONE FOR LAPAROSCOPIC SLEEVE GASTRECTOMY  |
| Principal Investigator Name/Contact Info: | [name] MD
[contact]   |
| Primary Contact Name/Contact Info         | [name] MD
[contact]
[contact]
[name] MD
[contact]
[contact]
[name] MD
[name] MD
[name] DO
[name] MD |
| Date Revised:                             | 1/10/2018  |
| Study Number:                             | IF 2203362   |

2018-2019 and subsequent data analysis. The subject's participation will be from time of enrollment in the pre-operative period until first 48 hours after surgery. Estimated date of enrollment completion will be when 110 eligible subjects are enrolled in final data analysis. Estimate date for study completion will be 2019.

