### j) Withdrawal of Subjects

Patients are free at any time to withdraw from the study. If they do so, their information will not be included in the study.

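### Enrolment closes on a count of patients analysed, and withdrawn patients are removed, so the 110 analysed need not be the randomised sample

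*Protocol*

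**What the plan says.** Four places in the protocol bear on this point.

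- **Section 5 c), Number of Subjects**, gives 110 and bases it on a power analysis: "two-tailed, with effect size of 0.7 (mild-moderate effect), alpha error 0.05, power 0.95". It makes no allowance for loss.
- **Section 4, Resources**, judges feasibility on the same figure: "For n=110, the feasibility of recruitment is manageable as we perform 5-10 sleeve gastrectomies per week on average".
- **Section 5 d), Study Timelines**, ties the end of enrolment to the analysis: "Estimated date of enrollment completion will be when 110 eligible subjects are enrolled in final data analysis". It also gives one year for the study and an estimated completion in 2019.
- **Section 5 j), Withdrawal of Subjects**, says of patients who withdraw: "If they do so, their information will not be included in the study".

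The protocol does not separate the number randomised from the number analysed. It states neither a replacement rule nor a maximum number to randomise.

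**The concern.** The number randomised and the number analysed are equal only if nobody is lost. Once someone withdraws, section 5 j) takes that patient out of the data and section 5 d) keeps enrolment open until another fills the count. The analysed group then consists of those who stayed, topped up to 110.

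Randomisation protects the comparison of everyone randomised. It does not protect a comparison of completers when leaving is related to both arm and outcome. The primary outcome is opioid use over 48 hours. A patient in more pain uses more opioid and may also be readier to leave. If that happens more in one arm, that arm looks better than it is.

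If 110 is instead a fixed total to randomise, as section 5 c) can be read, nobody is replaced but fewer than 110 are analysed, and the stated power no longer applies exactly.

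**Working it through.** **Inputs.** From section 5 c): effect size 0.7, two-sided alpha 0.05, power 0.95, total 110. Two things are assumed: 1:1 allocation (section 5 names two randomised groups but no ratio), and 0.7 as a standardised mean difference. The protocol states no loss rate, so 5% to 20% is used as a range.

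**Step 1: reproduce 110.** Normal approximation per arm: n = 2(1.960 + 1.645)² / 0.7² = 2 × 13.0 / 0.49 = 53.04, rounded up to 54 (108 in total). The two-sample t-test (noncentral t) needs 54.02, rounded up to 55 per arm, which is exactly 110. So 110 is the number to be analysed, with nothing added for loss.

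**Step 2: if 110 is the number randomised and losses are dropped.** Power of the t-test at d = 0.7:

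| Analysed | Split | Power |
|---|---|---|
| 110 | 55 + 55 | 95.3% |
| 109 | 55 + 54 | 95.2% |
| 108 | 54 + 54 | 94.99% |
| 104 (about 5% lost) | 52 + 52 | 94.2% |
| 99 (10% lost) | 50 + 49 | 93.2% |
| 88 (20% lost) | 44 + 44 | 90.1% |

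**Step 3: if enrolment runs until 110 are analysed.** Number randomised = 110 / (1 − loss). At 5% loss, 110 / 0.95 = 115.8, so 116. At 10%, 110 / 0.90 = 122.2, so 123. Power is kept under this reading.

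**Step 4: bias under an assumed pattern of loss.** Suppose there is no true effect. In both arms, 10% of patients have mean opioid use s SD above the other 90%, and in the QL 2 arm only, that 10% leaves.

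- The remaining QL 2 patients average 0.10 × s SD less than the control arm: 0.10 SD at s = 1 and 0.15 SD at s = 1.5. Against the planned effect of 0.7 this is 0.10 / 0.7 = 14% and 0.15 / 0.7 = 21%, in favour of QL 2.
- The control arm's variance is 1 + 0.10 × 0.90 × s², which is 1.09 and 1.20.
- With about 55 per arm analysed, the standard error is √(1/55 + 1.09/55) = 0.195 and √(1/55 + 1.20/55) = 0.200. The shift in standard errors is 0.10 / 0.195 = 0.51 and 0.15 / 0.200 = 0.75.
- With a critical value of 1.98, the two-sided rejection rate is about 7.7% and 11.2%.

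Simulation of the same scenario gives:

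| Rule | s = 1 | s = 1.5 |
|---|---|---|
| Losses dropped and replaced until 110 are analysed | 8.0% | 11.3% |
| 110 randomised, losses dropped, no replacement | 7.8% | 10.5% |

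Replacement therefore adds 0.2 and 0.8 points. If all 110 randomised patients are analysed as assigned, with outcomes obtained, the simulated rate is 4.9%. Under the replacement rule about 116 are randomised on average, because a 10% loss in one arm is 5% overall.

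**The case against.** The strongest objection is that the harm belongs to the withdrawal rule, since dropping patients without replacing them gives nearly the same false-positive rate. This stands. A reader might infer that the enrolment rule itself causes the bias, or that the bias would persist if withdrawn patients' data were kept. The calculation supports neither. Section 5 j) is the only stated rule that takes a patient out of the analysis. Section 6 says the block is discontinued if the needle cannot be seen properly, but not that such a patient leaves the analysis.

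A second objection is that section 5 d) only estimates a date, that eligible may simply mean meeting the entry criteria, and that replacement is never mentioned. This stands in part. Replacement is an inference, but it follows from ending enrolment on an analysed count while withdrawn patients are removed from it. A reader might infer replacement without limit; the protocol gives no numerical ceiling but does give an estimated end in 2019. A reader might also infer that losses would be concealed. Nothing says that the numbers randomised or withdrawn will go unreported.

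A third objection is that the power loss is trivial, and it largely is. Power drops below 95% at the second loss, but only to 94.99%, and is still 90.1% at 20% loss. Follow-up lasts only 48 hours, which gives no obvious reason to expect heavy loss. The bias from replacing losses and the power shortfall are also alternatives: if enrolment runs to 110 analysed, power is kept.

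Last, analysis sets and missing-data methods are commonly left to the SAP. That is fair for their detail. But the enrolment stop and the removal of withdrawn patients are fixed in this protocol, and a later plan cannot change how enrolment was run.

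**Conclusion.** The point holds in a limited form. Sections 5 d) and 5 j), followed together, produce a completers-only sample topped up to 110, while section 5 c) presents 110 as the number of subjects.

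If loss is related to arm and opioid use, the primary comparison is biased. In the assumed scenario false positives are about 8% to 11% against a nominal 5%. That size depends on the assumed 10% loss, confined to QL 2 and to patients with opioid use 1 to 1.5 SD higher. If loss is unrelated to opioid use, this bias does not arise. Nearly all of it comes from the exclusion, with less than 1 point from the implied replacement.

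The power effect is minor and arises only if 110 is a fixed number randomised. The power figures also assume 1:1 allocation and a t-test on a standardised difference, which the exact reproduction of 110 supports.

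**What to change.** - **Section 5 d).** Replace the enrolment sentence with: *Enrolment closes when 110 patients have been randomised; randomised patients are not replaced; all randomised patients are analysed in their assigned arm.* Being eligible should no longer be a condition for counting a randomised patient.
- **Section 5 j).** Align it so that data collected on withdrawn patients are kept where consent allows.
- **Section 5 c).** State that 110 is the number randomised and that 95% power assumes no loss, with about 94% at 5% loss and 93% at 10%.

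The cost is a few sentences and no extra patients. The stated power becomes slightly less favourable if any outcomes are missing. The change protects the false-positive rate only as far as outcomes of patients who leave are actually obtained.

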### e) Study Endpoints

Primary outcome: The amount of opioid consumption (in mg IV morphine equivalents) postoperatively during the first 48 hours after the procedure.

Secondary outcome: VAS pain scores on arrival to PACU and at 1, 2, 24, and 48 hours. VAS scores on ambulation on the floors. Extent of blockade as determined by pin prick, itching, nausea, vomiting in PACU.

Respiratory rate, heart rate, and blood pressure will be recorded on arrival, 1 hour after arrival to PACU and then on departure from PACU.

Time to first dose of opioid administration, PACU length of stay, location of pain.

### f) Procedures Involved in the Human Research

|   |   |  |
|---|---|--|
|  | Protocol Title:                           | QUADRATUS LUMBORUM II BLOCK VS CONVENTIONAL THERAPY ALONE FOR LAPAROSCOPIC SLEEVE GASTRECTOMY  |
|   | Principal Investigator Name/Contact Info: | [name] MD
[contact]   |
|   | Primary Contact Name/Contact Info         | [name] MD
[contact]
[contact]
[name] MD
[contact]
[contact]
[name] MD
[name] MD
[name] DO
[name] MD |
|   | Date Revised:                             | 1/10/2018  |
|   | Study Number:                             | IF 2203362   |
|   |   |  |

Patients will be randomized to receive either QL 2 block or standard therapy, which consists of the injection of 30 mL of bupivacaine 0.25% directly into the incision site by the surgeon at the end of the procedure. The QL 2 group will receive 15 mL bupivacaine 0.25% on both sides for a total of 30 mL.

All patients will receive general anesthesia (GA) with an endotracheal tube. Patients will be brought to the operating room and general anesthesia will be induced with midazolam 1-2 mg, fentanyl 1-2 mcg/kg, propofol 2-3 mg/kg, and succinylcholine 0.6 mg/kg followed by intubation of the trachea.

For the QL 2 group, after the surgical procedure is finished and before extubation, the abdomen will be sterilized with chlorhexidine prep and time out performed according to universal protocol. A curved, low frequency probe (5-8 MHz) with an imaging depth set between 1-9 cm will be used. For the QL 2 block, the probe will be placed at the anterior superior iliac spine at the level of the mid-axillary line and moved cranially until the three muscles of the abdominal wall: external oblique, internal oblique, and transversus abdominis (from superficial to deep) are identified. The probe will then be moved postero-laterally until the posterior border of the external oblique is visualized. At this point, the internal oblique forms a roof over the quadratus lumborum and the middle layer of the thoracolumbar fascia can then be visualized as a hyperechoic band investing the quadratus lumborum muscle. A

|   |  |
|---|--|
| Protocol Title:                           | QUADRATUS LUMBORUM II BLOCK VS CONVENTIONAL THERAPY ALONE FOR LAPAROSCOPIC SLEEVE GASTRECTOMY  |
| Principal Investigator Name/Contact Info: | [name] MD
[contact]   |
| Primary Contact Name/Contact Info         | [name] MD
[contact]
[contact]
[name] MD
[contact]
[contact]
[name] MD
[name] MD
[name] DO
[name] MD |
| Date Revised:                             | 1/10/2018  |
| Study Number:                             | IF 2203362   |

10 cm, 21-gauge block needle will be inserted from an anterior to posterior direction followed by injection of 15 mL of bupivacaine 0.25% on each side for a total of 30 mL.

All patients will receive IV acetaminophen 1000 mg and IV ketorolac 30 mg, as well as, fentanyl 25-50 mcg prn for intraoperative pain when the HR and/or SBP increase to above 20% of baseline. Postoperatively, all patients will receive acetaminophen 1000 mg IV q6h for a total of 4 doses, ketorolac 15 mg IV q6h for a total of 4 doses, and hydromorphone 0.3 mg IV q4h prn for severe pain (>6 on the VAS pain scale).

Patients will be evaluated by research personnel who are blinded as to which treatment the patient received. The first evaluation will be on arrival and one hour after arrival in the PACU. This will consist of sensory exam by pinprick to determine the extent of the block, VAS pain scores, opioid consumption, assessment of nausea and/or vomiting, and documentation of vital signs like respiratory rate, heart rate, and blood pressure will be recorded in PACU as well.

